#### Group Assignment:

All Participants: All participants in the study will receive the following:

Standardized Physical Therapy Rehabilitation: Participants will receive usual physical therapy rehabilitation provided by a licensed physical therapist using the University of Delaware's Rehabilitation Guidelines for Unilateral Total Knee Replacement. See attached documents for Rehab Practice Guidelines for: Unilateral Total Knee Replacement.

Home Exercise Program: Participants will be given a University of Delaware binder. Pictures and descriptions of the standardized home exercise program and exercise log are located in this binder. See attached documents for Home Exercise Program and Exercise Log.

Actigraph: Participants will be asked to wear an accelerometer called an ActigraphGT3X to objectively measure physical activity. The size of the Actigraph is 27g; 1.5" x 1.44" x 0.70". The Actigraph monitors physical activity in terms of steps per day and time spent in moderate to vigorous physical activity. Actigraph monitors will be disinfected prior to wear in accordance with EPA guidelines. The monitor will be worn around the participant's waist with the accelerometer located at the person's right anterior superior iliac spine (ASIS) and the participant will receive in-person instructions on how to properly wear this device. The Actigraph will be worn for approximately one week (7 days) after the patient enrolls in the study. Participants will also be asked to wear the monitor for approximately one week (7 days) after they discharge from formal physical therapy rehabilitation, at 6-months after discharge from formal physical therapy, and at 12-months after discharge from formal physical therapy. The patients will be instructed to put on the monitor when they get up in the morning and take off the monitor when they go to sleep in the evening. They will be asked to remove the monitor during situations that device could get wet, e.g., showering, swimming. See attached documents for Actigraph Instructions. If the device is lost or damaged the participant will notify their physical therapist or the physical activity research team for a replacement.

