7.1 Timing of Analyses

Final analyses will be performed when data collection is completed. In particular, the final analyses will be performed when all enrolled study subjects have completed the 12 month follow up or dropped out prior to the 12 month follow up. The final analysis will be performed on data transferred to a file from RedCap, having been documented as meeting the cleaning and approval requirements after the finalization and approval of this SAP document. In particular data cleaning will involve checking physical documents for errors/discrepancies, ensuring all responses are correctly entered into REDCap, and then performing a quality check to ensure answers were entered accurately. For the ActiGraph, we will ensure data was recorded at 60Hz, that data fell within the expected wear time range, and that included participants met our wear time criteria of at least 4 days and at least 10 hours on those days.

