7.2.1 Full Analysis Sample (Intention to Treat)

- All subjects who were randomized
- The ActiGraph monitor was worn for > 4 days of 10 hours of wear time each time point (baseline, discharge, and 6 months).
- This sample will be the primary efficacy sample

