7.2.2 Per Protocol Sample

- All subjects who adhere to the major criteria in the protocol
 - o Subjects who did not drop out
 - Completed Physical Therapy
 - Did not drop out over the 12 months of follow up after discharge from physical therapy
 - The ActiGraph monitor was worn > 4 days at each time point (baseline, discharge, 6 months, and 12 months).

The exact process for assigning the statuses (Full Analysis Sample and Per Protocol Sample) will be defined and documented prior to breaking the blind along with any predefined reasons for eliminating a subject from a particular population.

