8.3 Treatment Compliance

Characteristic [mean ± SD or n (%)]	All n=	Intervention n =	Control n =
Days Randomization to Discharge			
Days Eval to Discharge			

Characteristic [mean ± SD or n (%)]	Intervention n =
Percent of days in PT in the study that the Fitbit was checked (recorded or checked on HEP):	
Percent of weeks in PT in the study that a step goal was recorded:	

9 Efficacy Analyses

The primary and secondary outcomes will be summarized stratified by treatment group at each study timepoint (baseline, discharge, 6-month, 12-month). Our primary analysis will use an intention-to-treat (ITT) analysis that includes all participants who wore the monitor for \geq 4 days at baseline. The statistical model underlying the analysis a mixed-effects model to examine the main and interaction effects of *group* (Intervention vs. Control) and *time* (BL, DC, 6M, and 12M) on MVPA (minutes/day). We will adjust this model for age, sex, and body mass index. The null hypothesis is that there is no difference in change in MVPA in the intervention group compared to the control group. The alternative hypothesis is that there is a difference between groups. The nature of the hypothesis is confirmatory as this study has been powered to detect a difference should one exist. The mixed-effect model will be used to calculate the mean and 95% Confidence Interval time in MVPA at each study time point. We will also calculate difference in means and 95% Confidence Intervals between the intervention and control group at each study time point. We will also calculate 2-sided p-values to determine statistical significance of differences between groups by time in MVPA.

• Methods and assumptions for handling longitudinal data or missing data.

Mixed-effect modeling will be used to estimate MVPA over time. The mixed-effect model using restricted maximum likelihood estimation is a full information approach and leads to unbiased model parameter estimates in the presence of MCAR or MAR missingness. Selection between two common covariance structures, Toeplitz and AR(1), will be accomplished using the Akaike Information Criterion (AIC).

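### The SAP states its ActiGraph wear rule in four inconsistent ways, two of them defining the same primary ITT analysis, and never says what happens to a single visit with too little wear

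*SAP*

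**What the plan says.** The wear rule appears in four places in the SAP.

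- **Section 7.1** (data cleaning): the team will check that "included participants met our wear time criteria of at least 4 days and at least 10 hours on those days". No visit is named. The same sentence adds a check that the data fall in an expected wear-time range, which is not defined.
- **Section 7.2.1** (full analysis sample, labelled intention to treat): "The ActiGraph monitor was worn for > 4 days of 10 hours of wear time each time point", with baseline, discharge and 6 months listed. The section adds: "This sample will be the primary efficacy sample".
- **Section 7.2.2** (per-protocol sample): "The ActiGraph monitor was worn > 4 days at each time point (baseline, discharge, 6 months, and 12 months". No hours are given.
- **Section 9** (efficacy analyses): the primary ITT analysis "includes all participants who wore the monitor for \geq 4 days at baseline". No hours are given, and no later visit is mentioned.

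The variable table in Section 6.4 says that MVPA and steps/day are calculated from the monitor. It does not say which days count or how many are needed. The protocol (Group Assignment) says "The Actigraph will be worn for approximately one week (7 days) after the patient enrolls in the study", asks for about a week of wear at the later time points too, and gives no minimum.

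**The concern.** MVPA in minutes/day is the primary outcome, so the wear rule decides which values exist and who is analysed. Three things are at stake.

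First, Sections 7.2.1 and 9 both claim to define the primary ITT analysis. They differ on the number of days, the hours and the visits covered, so an analyst cannot follow both.

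Second, the rules are written as conditions for including a participant. Nothing says that a visit with too little wear is set to missing. Section 9 as written keeps a participant with adequate baseline wear and sets no minimum for what that person contributes later. Time when the monitor is off cannot count towards MVPA or steps, so short-wear days tend to understate both. The mixed model can accommodate a missing visit. It cannot correct a low value that is treated as observed.

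Third, 7.2.1 goes to the other extreme: one failing visit removes the whole participant. That works against Sections 7.4 and 9, which choose restricted maximum likelihood because it can use participants with incomplete follow-up.

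**Working it through.** **Step 1. The four rules side by side.**

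| SAP section | Days | Hours per day | Time points |
|---|---|---|---|
| 7.1 | 4 or more | 10 or more | none named |
| 7.2.1 (ITT) | more than 4 | 10 | baseline, discharge, 6 months |
| 7.2.2 (per protocol) | more than 4 | none | all four |
| 9 (primary ITT) | 4 or more | none | baseline |

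On days and hours alone, the four statements fill every cell of a two-by-two table.

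**Step 2. Test records, reading each section literally.** Wear is a full week at every visit except as stated.

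| Record | 7.1 | 7.2.1 | 7.2.2 | 9 |
|---|---|---|---|---|
| Baseline: exactly 4 ten-hour days | passes | out | out | in |
| Baseline: five 3-hour days | fails | out | in | in |
| 6 months: two short days | fails only if applied at that visit | out entirely | out | in, 6-month value kept |
| 12 months: two short days | fails only if applied at that visit | in, 12-month value kept | out | in, 12-month value kept |

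The second row shows that the per-protocol sample can admit a record that the ITT sample rejects. The fourth row matters because Mock Tables 1 and 2 report 12-month values in the ITT sample, while 7.2.1 sets no wear condition at 12 months.

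**Step 3. Scale of the 4-day boundary (illustration only).** The plan has no figure to reproduce: it gives no wear distribution, and N = 120 (SAP Section 7) is stated without inputs. Take 7 days of wear (protocol) and assume that each day is independently valid with probability p. Then

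P(exactly 4 valid days) = C(7,4) × p⁴ × (1−p)³ = 35 × p⁴ × (1−p)³.

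- p = 0.80: 35 × 0.4096 × 0.008 = 0.115, or about 13.8 of 120 records at one visit.
- p = 0.90: 35 × 0.6561 × 0.001 = 0.023, or about 2.8 of 120.
- p = 0.95: 35 × 0.8145 × 0.000125 = 0.0036, or about 0.4 of 120.

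**Step 4. Scale of the missing 10-hour condition at baseline (illustration only).** Let w be the assumed probability that a day is worn at all, and q the probability that a worn day reaches 10 hours. The extra records admitted by omitting the hours are 120 × [P(Bin(7, w) ≥ 4) − P(Bin(7, wq) ≥ 4)].

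- w = 0.8, q = 0.8: 120 × (0.967 − 0.783) = about 22.
- w = 1.0, q = 0.9: 120 × (1 − 0.9973) = about 0.3.

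Both ranges run from negligible to material, and the documents do not say where this trial lies.

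**The case against.** **Section 7.1 governs, and the rest is shorthand.** It calls the rule the team's own criteria, and it adds the wear-range check. If applied at every visit to every sample, it would block short-wear values. This is the best argument for adopting that rule. It does not settle the matter, because 7.1 names no visit, leaves the range undefined, and differs from 7.2.1 on the number of days.

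**The defined primary sample already excludes short wear.** This is true under 7.2.1 for baseline, discharge and 6 months. A reader might infer from Section 9 that short-wear 6-month values will enter the primary analysis. The documents support only that they could, if Section 9 is followed literally and the 7.1 check is not applied at that visit.

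**The > may be a ≥ that lost its bar when the PDF was read.** This is possible. The SAP text keeps ≥ in Sections 7.3, 9 and 9.3, which makes it less likely but does not exclude it. If it is an artefact, the exactly-4-day conflict and Step 3 fall away. The conflicts over hours and visits, and the missing visit-level rule, remain.

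**Sample membership is settled blind.** Section 7.2.2 requires the assignment process and exclusion reasons to be documented before the blind is broken, and Section 7.5.4 has a blinded statistician fill in tables with unlabelled groups. A reader might infer that the sample could be chosen to suit the result; these safeguards do not support that. They still leave conflicting written definitions to reconcile.

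**Bias between arms.** A reader might infer that controls, who are given no Fitbit, would wear the ActiGraph less and so appear less active. The documents do not show this. Both arms receive the same ActiGraph instructions, reminder calls and wear-linked payments, and the protocol expects that some participants already own a tracker.

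**Large sample loss.** Requiring validity at three visits enlarges the boundary effect: at p = 0.8, 108 participants pass with 4 or more days against 74 with more than 4, of 120. At p = 0.95 it is 120 against 119. These counts assume independent days and visits and no dropout, so they are not a forecast.

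**Conclusion.** The inconsistency stands on the text. The SAP has four wear rules, and two of them define the primary ITT analysis differently in days, hours and visits. As written, the plan cannot be followed for a participant with exactly 4 valid baseline days (unless > means ≥), for one whose baseline days fall short of 10 hours, or for one whose wear is adequate at baseline but too short at discharge or 6 months.

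The effect on the treatment comparison cannot be derived, because the documents give no wear distribution, standard deviation or effect size. The only scale available is assumed: exactly 4 valid days in about 11.5% to 0.4% of weeks for p from 0.8 to 0.95. Short-wear values entering the analysis, and wear that differs by arm, are possibilities and are not shown. The point should be corrected before unblinding; it is not evidence that the result will be biased.

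**What to change.** 1. In Section 7.1, define validity once, using the sponsor's own threshold: a visit is valid if it has "at least 4 days and at least 10 hours on those days", and MVPA and steps/day for that visit are averaged over those days only. State that this applies at all four time points.
2. State that a visit failing the rule is set to missing for that visit only, and is handled by the mixed model. The missingness summaries by group and time planned in Section 7.4 would then show whether wear failure differs by arm.
3. In Section 7.2.1, replace the all-time-points wear condition so that a failing follow-up visit no longer removes the participant. To agree with Section 9, the condition would be a valid baseline visit.
4. Cite the 7.1 rule in 7.2.1, 7.2.2 and 9 in place of the separate day counts. Section 7.2.2 can still require a valid visit at every time point, with the 10-hour condition now included.

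**Cost.** No new data are needed. Some short-wear visit values become missing, and the estimates then rely on the missing-at-random assumption already made in Section 7.4. Item 3 changes the definition of the primary sample, so it is more than a wording edit. It should be recorded as a dated SAP amendment before the blind is broken.

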7.2.2 Per Protocol Sample

- All subjects who adhere to the major criteria in the protocol
 - o Subjects who did not drop out
 - Completed Physical Therapy
 - Did not drop out over the 12 months of follow up after discharge from physical therapy
 - The ActiGraph monitor was worn > 4 days at each time point (baseline, discharge, 6 months, and 12 months).

The exact process for assigning the statuses (Full Analysis Sample and Per Protocol Sample) will be defined and documented prior to breaking the blind along with any predefined reasons for eliminating a subject from a particular population.

7.3 Covariates and Subgroups

(ICH E3; 9.7.1, 11.4.2.1. ICH E9; 5.7)

We have identified three covariates that are expected to have an important influence on our study outcomes, i.e., age, sex, and body mass index. We will adjust for these covariates in all analyses. In particular, age and body mass index will be treated as continuous variables, and sex as a categorical variable. We will perform separate subgroup analyses to examine evidence for a difference in treatment effects based on 1) Age (< and \geq 65 years), 2) Sex (men and women), and 3) BMI (< and \geq 32 kg/m2).

SAP version 1.0: Physical Activity Intervention after TKR 3/16/23

7.4 Missing Data

(ICH E3; 9.7.1, 11.4.2.2. ICH E9;5.3. EMA Guideline on Missing Data in Confirmatory Clinical Trials)

Missing data will be given careful attention in the analysis. In this RCT we have two treatment arms and four fixed times tied to the recovery process for measurements. It is anticipated that drop-outs from the study will be limited because all have elected to undergo knee replacement surgery and would be working toward recovery. However, it is possible that participants may not attend all follow-ups. Drastically fewer participants in the final analysis would affect study sensitivity and excessive missed follow-ups would potentially bias model parameter estimates. Under the assumption of limited data that is missing completely at random (MCAR) or missing at random (MAR), the mixed-effect model using restricted maximum likelihood estimation is a full information approach and leads to unbiased model parameter estimates. Selection between two common covariance structures, Toeplitz and AR(1), will be accomplished using the Akaike Information Criterion (AIC).

In the event that assumptions are not met regarding missing value frequency, MAR, or MCAR and missing values are occurring with higher frequency or are truly missing not at random (MNAR), the analysis may be biased. To test the missingness assumptions, missing data will first be summarized by group, time, each design cell, and each of the three covariates, age, sex and body mass index in an effort to graphically or tabularly detect patterns in the variation of missingness. More formally, missing/nonmissing will be taken as a dichotomous outcome in a logistic regression for continuous covariates and will be compared with between and within factors and sex using chi-square tests. Significant logistic regression that will be identified and reported and whose impact on the analysis will be explained if possible.

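### The missing-data checks in SAP 7.4 cannot show whether data are MAR or MNAR, and no planned analysis shows whether the 6-month MVPA result survives MNAR dropout

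*SAP*

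**What the plan says.** SAP section 9 (Efficacy Analyses) justifies the REML mixed model on the ground that it "leads to unbiased model parameter estimates in the presence of MCAR or MAR missingness". Section 7.4 makes the same argument and names what could fail: "In the event that assumptions are not met regarding missing value frequency, MAR, or MCAR". It accepts that if values "are truly missing not at random (MNAR), the analysis may be biased".

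The response in section 7.4 has three parts:

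- A tabular or graphical look: "To test the missingness assumptions, missing data will first be summarized by group, time, each design cell, and each of the three covariates", these being age, sex and BMI.
- Formal tests: "missing/nonmissing will be taken as a dichotomous outcome in a logistic regression for continuous covariates", with chi-square tests for the between and within factors and for sex.
- A consequence: significant findings "will be identified and reported and whose impact on the analysis will be explained if possible".

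Section 7.4 expects limited drop-out but gives no rate. The protocol has no missing-data plan. Two other analyses touch the primary endpoint: the per-protocol analysis (SAP 7.2.2 and 9.2.1) and a repeat without data collected outside the visit windows (SAP 6.4).

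The SAP defines the primary sample in two ways. Section 7.2.1 requires valid monitor wear at baseline, discharge and 6 months. Section 9 requires it at baseline only.

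**The concern.** MAR and MNAR differ only in whether missingness still depends on the unobserved MVPA once the observed data are taken into account. No test on observed variables can settle that. Group, time, age, sex and BMI are all terms in the model, so missingness that depends on them is compatible with MAR and is not in itself a source of bias. A significant test therefore need not signal a problem, and a non-significant one gives no assurance about MNAR. The observed variable that bears most directly on MAR, earlier MVPA, is not in the listed checks.

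MNAR is plausible in this trial. The 6- and 12-month outcomes depend on a participant wearing a mailed ActiGraph for a week and posting it back (protocol, Procedures, under thank-you notes and phone calls). At least 4 days of 10 hours are required (SAP 7.1), and participants know their arm (SAP 6.1 and 6.3). Less active people may return fewer valid records, possibly to a different degree in each arm. Section 9 calls the hypothesis confirmatory. A reader of the result will want to know how strong such a mechanism would have to be to change the conclusion, and no planned analysis says.

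**Working it through.** **1. What each planned item can show**

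| Item | Can show | Cannot show |
|---|---|---|
| Table by group, time and design cell (7.4) | Frequency; unequal return by arm or visit | Why values are missing |
| Logistic and chi-square tests (7.4) | Evidence against MCAR | MAR versus MNAR |
| Per-protocol analysis (7.2.2, 9.2.1) | Result among those who stayed and wore the monitor at every visit | Effect of those who left; it conditions further on follow-up |
| Out-of-window exclusion (6.4) | Sensitivity to visit timing | Effect of values never collected |

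No row varies the MAR assumption.

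**2. Reference difference.** The SAP states N = 120 (section 7) but no alpha, power, effect size or SD, so that figure cannot be reproduced. Assume 60 per arm, two-sided alpha 0.05 and 80% power:

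(1.960 + 0.842) × √(2/60) = 2.802 × 0.1826 = 0.51 SD; with the t distribution, 0.516, or about 0.52 SD.

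**3. Size of MNAR bias.** Let f be the share missing at 6 months and δ the amount, in SD, by which the missing values lie below the MAR prediction. Then

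bias in the group difference = −(f_I × δ_I − f_C × δ_C), for intervention (I) and control (C).

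If only the intervention arm is affected, the size is f × δ (all values assumed):

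- 10% × 0.3 = 0.03 SD
- 20% × 0.5 = 0.10 SD; 0.10/0.516 = 19% of the detectable difference
- 25% × 0.75 = 0.19 SD

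If share and shift are the same in both arms, the terms cancel and the bias is zero.

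**4. When this could change a conclusion.** To cancel a full 0.51 SD effect, δ would have to be 0.511/0.10 = 5.1 SD at 10% missing, 0.511/0.20 = 2.6 SD at 20%, or 0.511/0.30 = 1.7 SD at 30%. The exposed case is a borderline result. The standard error of a simple 60-versus-60 comparison is √(2/60) = 0.183 SD, so a 0.10 SD bias is 0.10/0.183 = 0.55 standard errors. With that standard error held fixed, a z statistic between 1.96 and 1.96 + 0.55 = 2.51 would lose significance.

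**5. Simulation of the tests.** Assumptions: 3,000 runs per scenario, N = 120, three visits with correlation 0.6, about 20% missing at 6 months, no true effect, and an estimator valid under MAR. Age, sex and BMI were generated independently of MVPA. Four tests were run at 0.05 (age, BMI, group, sex).

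| Mechanism | At least one test significant | Bias (SD) |
|---|---|---|
| MCAR | 0.193 | about 0 |
| MAR, differing by arm | 0.181 | about 0 |
| MNAR, alike in both arms | 0.181 | about 0 |
| MNAR, opposite direction by arm | 0.176 | 0.20 |

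The chance rate for four independent tests is 1 − 0.95⁴ = 0.185. In these scenarios the tests behave the same whether the missingness is harmless or harmful. The last scenario is deliberately adverse, and missing rates were similar across arms throughout, so unequal return was not examined.

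**The case against.** Several points on the other side stand.

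- A reader might infer that the SAP claims to test MAR against MNAR, using three covariates only. The text does not say that. It speaks of missingness assumptions, which include frequency and MCAR, and it also uses group, time and design cell. Frequency and MCAR can be examined this way; MAR cannot.
- A reader might infer that a significant test triggers a wrong analysis. It does not. Results are reported and their impact is "whose impact on the analysis will be explained if possible"; the primary analysis stays as it is.
- The existing table would reveal unequal return by arm and visit, though not its cause.
- Leaving earlier MVPA out of the checks does not bias the mixed model, because observed MVPA is part of its likelihood.
- The plan works to limit missing data. It excludes people with no interest in more activity, and provides thank-you notes, reminder calls, prepaid return envelopes and gift cards. Participants who stop the intervention stay in follow-up. These steps should reduce missingness, but they cannot establish that what remains is MAR.
- The bias figures are assumed. The central 0.10 SD is about half a standard error, and the direction and degree by arm are unknown.

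None of this supplies an analysis that departs from MAR.

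**Conclusion.** The concern holds in a limited form. Section 7.4 presents as a test of its assumptions a set of checks that cannot bear on MAR versus MNAR, and the SAP plans no analysis of how the 6-month MVPA difference would change under MNAR. The documents do not support the stronger inference that the result is biased: they give no missing rate, and bias is near zero if MNAR acts alike in both arms. The illustrative bias of 0.10 SD (0.03 to 0.19 SD) rests on assumed missing shares and on shifts confined to the intervention arm. The 0.52 SD reference rests on assumed alpha, power and equal arms. On those figures a large effect would be safe and a borderline one would not.

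The bias calculation also presumes the section 9 sample. Under section 7.2.1 the primary analysis is complete-case: anyone without valid wear at all three visits is left out, and the MAR argument for REML does not operate. The change should be made, but it does not call the primary model itself into question.

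**What to change.** 1. Reconcile SAP 7.2.1 with section 9 first. Only a sample that keeps participants with missing discharge or 6-month wear lets the MAR argument operate and leaves values to impute.
2. In section 7.4, keep the table by group, time and design cell, add baseline and last observed MVPA as predictors of missingness, and reword the passage as a description of missingness, not a test of MAR.
3. Pre-specify one MNAR sensitivity analysis of the 6-month MVPA difference. Multiply impute using arm, age, sex, BMI and all observed MVPA. Then apply a delta to the imputed intervention-arm values and increase it until the conclusion changes (tipping point). Report that delta in minutes per day so that readers can judge its plausibility. Control-based imputation is an optional addition.

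The cost is SAP wording and modest programming. No new data are needed and the mixed model is unchanged; step 1 settles which participants enter it. The change should be in place before the blind is broken, when section 7.2.2 already requires sample membership to be documented.
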